APPENDIX F: SCHEDULE OF VISITS & MEASUREMENTS: Group 18.....	42
APPENDIX G: SCHEDULE OF VISITS & MEASUREMENTS: Group 15	43
APPENDIX H: OBLIGATIONS OF THE INVESTIGATOR.....	44
APPENDIX I: DECLARATION OF HELSINKI	46

CLINICAL PROTOCOL

Date:

Protocol No.:
IDOS-402-IVTV

SYNOPSIS

This is a prospective, open-label, single center, clinical study of the Travoprost Intraocular Implant, [REDACTED] (G2TR-125) in subjects diagnosed with open-angle glaucoma (OAG) or ocular hypertension (OHT). The purpose of this study is to evaluate [REDACTED] the performance of the Travoprost Intraocular Implant and the *in vivo* drug elution rate to be used to establish a correlation model and analysis.

The study is designed to enroll and implant [REDACTED] (approximately 210 total subjects). Subjects who meet criteria at Visit 1 (Screening) may be scheduled for surgery at Visit 2 during which they will be implanted with the G2TR-125 implant. Depending on the cohort, each subject will be followed for 3 – 24 months at which time the subject will undergo the exchange procedure consisting of removal of the implant and implantation of a new implant. At this visit, aqueous humor samples and the extracted implant will be collected. Following the exchange procedure, all subjects will be followed for an additional 4 weeks.

Test Article(s): Travoprost Intraocular Implant, [REDACTED] (G2TR-125)

STUDY OBJECTIVE

The objective of this study is to evaluate [REDACTED] the performance of the Travoprost Intraocular Implant and to study the drug elution rate *in vivo*, as derived from the residual drug in the explant of the Travoprost Intraocular Implant.

STUDY TREATMENT

Subjects will undergo implantation and exchange of a Travoprost Intraocular Implant (G2TR-125) through a small temporal clear corneal incision.

Structure: **Multiple cohort**

Number of Centers: Single center

Open-label

Method of Subject Assignment:

After Visit 1 (Screening), qualified subjects will be scheduled to undergo treatment with the model G2TR-125 implant.

Total Sample Size: Approximately 210 subjects

CLINICAL PROTOCOL

Date:
September 18, 2019

Protocol No.:
IDOS-402-IVIV

STUDY OVERVIEW

Subjects will be assessed for inclusion/exclusion criteria at Visit 1 (Screening). At this visit, all subjects must meet all entry criteria. Subjects who meet the eligibility criteria at Visit 1 (Screening) can be scheduled for Visit 2 (First Operative Day 0) on a separate day.

Visit Schedule:

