8.1 Sample Size

The sample size of 210 subjects who undergo implantation and exchange of a Travoprost Intraocular Implant was determined empirically. This sample size is considered adequate to provide information on the safety of the exchange procedure.

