9 ADVERSE EVENTS

An Adverse Event (AE) is defined as any untoward and unintended medical occurrence (e.g., sign, symptom, disease, syndrome) that occurs in a study subject, regardless of the suspected cause during the study. Adverse events will be clearly documented on the study source document and monitored throughout the course of the study.

Events occurring after signing the informed consent but prior to the implant procedure should be documented in the medical history. Events observed during or after the initial implant or exchange procedure until the final study visit, are to be recorded as AEs if they are in the study eye and deemed related to the implant or procedure.

CLINICAL PROTOCOL

Date:
September 18, 2019

Protocol No.:
IDOS-402-IVIV

Any clinically significant change in a subject's condition after receiving the study treatments, regardless of causality, is to be considered an adverse event, unless the change is determined to be a continuation of a pre-existing condition that is documented in the subject's medical history. If an adverse event occurs, an AE form must be completed.

An AE includes any of the following:

- An exacerbation or an unexpected increase in frequency or intensity of a pre-existing condition, including intermittent or episodic conditions
- New conditions or illnesses detected or diagnosed after the implant procedure
- A suspected interaction with any of the study treatments
- Signs, symptoms, or the clinical sequelae of a suspected overdose of either any of the study treatments or a concomitant medication
- Any clinically significant laboratory finding that was not present prior to receiving any of the study treatments

An AE does NOT include any of the following:

- Anticipated day-to-day fluctuations of any pre-existing conditions, including the disease under study (OAG and OHT).
- Medical or surgical procedure, (e.g., colonoscopy or hernia repair). The condition that led to the procedure may be an AE, if not present in medical history.
- Hospitalizations where an untoward medical occurrence did not occur (social or convenience admission to the hospital).
- Pre-existing conditions or diseases that were present before receiving any of the study treatments that do not worsen or that are chronic but stable
- Changes in a chronic condition or disease that are consistent with natural disease progression. (These medical conditions should be adequately documented).

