- Lack of efficacy of the study treatment for the condition being investigated.

AEs will be graded on a 3-point scale and reported in detail as indicated on the CRF:

Mild: easily tolerated, causing minimal discomfort and not interfering with normal everyday activities

Moderate: sufficiently discomforting to interfere with normal everyday activities

Severe: incapacitating and/or preventing normal everyday activities

CLINICAL PROTOCOL

Date:
September 18, 2019

Protocol No.:
IDOS-402-IVIV

The relationship of each AE to study treatment should be determined by the investigator using the following explanations:

Definitely Unrelated: the event is clearly related to other factors such as the subject's clinical state, therapeutic interventions, or concomitant medications administered to the subject

Unlikely Related: the event is most likely produced by other factors such as the subject's clinical state, therapeutic interventions, or concomitant medications administered to the subject; and does not follow a known response pattern to the study medication

Possibly Related: the event follows a reasonable temporal sequence from the time of drug administration; and/or follows a known response pattern to the study medication; but could have been produced by other factors such as the subject's clinical state, therapeutic interventions, or concomitant medications administered to the subject

Probably Related: the event follows a reasonable temporal sequence from the time of drug administration; and/or follows a known response pattern to the study medication; and is not likely to have been produced by other factors such as the subject's clinical state, therapeutic interventions, or concomitant medications administered to the subject

Definitely Related: the event follows a reasonable temporal sequence from the time of drug administration; and follows a known response pattern to the study medication; and cannot be reasonably explained by other factors such as the subject's clinical state, therapeutic interventions, or concomitant medications administered to the subject

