9.3 Suspected, Unexpected, Serious, Adverse Reaction (SUSAR)

A Suspected, Unexpected, Serious, Adverse Reaction (SUSAR) is any AE for which there is evidence to suggest a causal relationship between the Travoprost Intraocular Implant and the AE, and which is assessed as both unexpected and serious. An unexpected adverse reaction, i.e. any untoward and unintended response to any of the study treatments, is one for which the nature and severity is inconsistent with the applicable reference safety information (e.g., Investigator's Brochure).

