7.1.2. Adverse Events

Adverse events (AEs) will be coded to the MedDRA nomenclature, Version 21.0. Treatment Emergent Adverse Events (TEAEs) are defined as AEs that occur after the initiation of the first surgery at Visit 2 (First Operative Day 0).

AEs will be categorized into either the initial or PE study periods, as described in Section 2.3.1. AEs that extend between study periods (i.e., beginning during the initial study period and extending into the PE study period), will be categorized into the initial study period. However, if an increase in severity or change in relationship to study treatment occurs during the PE study period, the AE will be categorized into both the initial and PE study periods.

A summary of the number and percentage of subjects with TEAEs [REDACTED] will be provided for each study period. The summary will include study eye TEAEs, non-ocular or non-study eye TEAEs, treatment-related TEAEs, TEAEs by maximum severity, TEAEs resulting in study discontinuation, serious TEAEs, and deaths.

The number and percentage of subjects with study eye TEAEs, non-study eye TEAEs, and non-ocular TEAEs will be provided by SOC, PT, [REDACTED] for:

- TEAEs
- TEAEs related to study treatment
- TEAEs by maximum severity
- Serious TEAEs

Tabulations of study eye TEAEs for each of the above categories will be provided for each study period.

All AEs will be presented in a listing by subject. Separate listings for intraoperative AEs, serious adverse events (SAEs), AEs leading to deaths, AEs leading to study discontinuation, and AEs leading to removal of implant will also be presented.

Relationship to study treatment is defined as the possibility that the study treatment caused the event and is described in the study protocol. The relationship to study treatment categories utilized on the CRF are definitely unrelated, unlikely related, possibly related, probably related, and definitely related. For all tabulations presenting relationship to study treatment, the categories of possibly related, probably related, and definitely related will be classified as related and only related AEs will be presented. AEs with missing relationships are counted as related. Subjects experiencing more than one treatment related AE within a given SOC or PT will be counted once within that SOC or PT.

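### The adverse event causality scale rates relationship to study treatment by drug criteria alone, so the treatment-related tables can under-count or inconsistently count complications of the study procedures

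*Protocol*

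**What the plan says.** The synopsis, under Study Treatment, describes surgery: "Subjects will undergo implantation and exchange of a Travoprost Intraocular Implant (G2TR-125) through a small temporal clear corneal incision". Protocol section 9 records study-eye events from the implant or exchange procedure onwards "if they are in the study eye and deemed related to the implant or procedure".

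The same section then sets one causality scale: "The relationship of each AE to study treatment should be determined by the investigator using the following explanations". Its five categories run from Definitely Unrelated to Definitely Related. The positive criterion shared by Possibly and Probably Related is "the event follows a reasonable temporal sequence from the time of drug administration; and/or follows a known response pattern to the study medication"; Definitely Related requires both the timing and the response pattern. Definitely Unrelated is defined as "the event is clearly related to other factors such as the subject's clinical state, therapeutic interventions, or concomitant medications administered to the subject", and the same list of other factors recurs in the remaining four categories. No category names the device, the incision, the aqueous tap or the exchange.

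SAP 7.1.2 refers to the protocol for the meaning of relationship and states that "the categories of possibly related, probably related, and definitely related will be classified as related and only related AEs will be presented". An event with a missing relationship counts as related. The SAP has no relationship-to-procedure category.

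On sample size, Protocol 8.1 calls the 210 empirical and adds: "This sample size is considered adequate to provide information on the safety of the exchange procedure". Section 9.3 defines a SUSAR as an event for which "there is evidence to suggest a causal relationship between the Travoprost Intraocular Implant and the AE"; its next sentence speaks of a response to any of the study treatments.

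**The concern.** The object being rated (study treatment, including surgery) and the test applied to it (drug timing and drug response) do not match. Read literally, an event that the investigator is sure was caused by the surgical manoeuvre fits the definition of Definitely Unrelated, because surgery is a therapeutic intervention. Yet section 9 may have had the event recorded precisely because the procedure caused it.

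This matters because the study is open-label and non-randomized with no control group, and at Visit 7 the tap, the explantation and the second implantation take place in one session. The investigator's causality rating is the main planned means of telling procedure harm from drug or implant harm. Information on exchange safety is also the reason Protocol 8.1 gives for regarding 210 subjects as adequate.

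**Working it through.** **1. Walking a procedure complication through the scale.** Take an event that the investigator attributes to the incision, the tap or the exchange, with no known drug response pattern.

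| Category | What it requires | Can the event meet it? |
|---|---|---|
| Definitely Unrelated | Clearly due to other factors, including therapeutic interventions | Yes, if study surgery counts as an intervention |
| Unlikely Related | Most likely due to other factors, and no drug response pattern | Yes, on the same reading |
| Possibly Related | Reasonable timing from drug administration is enough; another cause is allowed | Yes, on timing alone |
| Probably Related | As above, and other factors not the likely cause | Not readily; only if study surgery is not an other factor |
| Definitely Related | Timing and drug response pattern, and no reasonable other explanation | No, because there is no drug response pattern |

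SAP 7.1.2 counts the last three categories as related. The same event is therefore inside or outside the related tables depending on how one undefined phrase is read.

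**2. Timing of the tap.** In Protocol 6.3.4.7 the aqueous sample is step 6 and the exchange is step 9. A tap injury thus precedes the second implant and comes 3 to 24 months after the first. Whether it follows drug administration in a reasonable sequence is a matter of opinion, so even the Possibly Related route is weaker here than for an implantation event.

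**3. Number of procedures.** The data analysis plan (section 2.3) gives 14 × 15 = 210 subjects, which agrees with the stated total. If all complete, there are 210 × 2 = 420 surgeries and 210 taps.

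**4. Illustration of size.** The documents give neither a complication rate *p* nor the share *m* of such events rated Unlikely or Definitely Unrelated. Both are assumed.

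Expected subjects in the related table = 210 × p × (1 − m). Chance that the table shows at least one = 1 − [1 − p(1 − m)]^210.

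| p | m = 0 | m = 25% | m = 50% | m = 75% | m = 100% |
|---|---|---|---|---|---|
| 2%: expected | 4.2 | 3.2 | 2.1 | 1.1 | 0 |
| 2%: chance of at least one | 98.6% | 95.8% | 87.9% | 65.1% | 0 |
| 5%: expected | 10.5 | 7.9 | 5.3 | 2.6 | 0 |
| 5%: chance of at least one | >99.9% | >99.9% | 99.5% | 92.9% | 0 |

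With every event counted, 210 subjects show at least one case with 95% probability when the true rate is 1 − 0.05^(1/210) = 1.42% or more. If 75% are rated unrelated, the related table needs a true rate of 1.42% / 0.25 = 5.7% to do the same. The all-causality counts are the same in every column.

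**The case against.** The best case for the plan has three parts.

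First, if study treatment means implantation and exchange, then other factors should mean factors other than these, and the study surgery would not count against relatedness. That is a sensible reading and many investigators may adopt it. But no sentence states it, and it leaves the positive criteria untouched: they still ask only about the drug.

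Second, a reader might infer that surgical complications are systematically removed from the related tables. The documents do not support that. Possibly Related is met on timing alone, tolerates another cause, and counts as related. The implant is placed at surgery, so most peri-operative events do follow drug administration, and missing ratings count as related. What stands is ambiguity with a risk of under-attribution.

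Third, exchange safety is reported by many routes with no causality filter. Study-eye TEAEs, their severity and serious TEAEs are tabulated by study period, and the post-exchange period includes the exchange procedure itself (SAP 2.3.1, 7.1.2). Intra-operative events are summarized separately under Protocol 8.5.1 and listed in the SAP. Change from pre-exchange is summarized for visual acuity, slit lamp, gonioscopy and IOP (SAP 7.1.3). This stands in full for recorded events, and it confines the problem to the related tables. These outputs do not, however, attribute cause.

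Two further inferences go too far. The trial was not sized for exchange safety: the 210 was empirical, and SAP 2.4 says it does not rest on a power calculation. Nor is the SUSAR definition confined to the implant, since its second sentence covers any study treatment; the two sentences are merely inconsistent. All serious events must be reported to the sponsor whatever their cause (Protocol 9.1).

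**Conclusion.** The wording defect is real and conflicts with the synopsis and with the recording rule in section 9. It allows a procedure-caused event to be rated from Definitely Unrelated to Possibly Related and makes the two higher categories hard to reach. The treatment-related TEAE tables can therefore under-count such events or count them inconsistently. The size cannot be estimated from the documents: under an assumed 5% complication rate the related table could show 0 to 10.5 of 210 subjects, and under 2%, 0 to 4.2. These ranges show what rating convention alone can do; they do not forecast misclassification. Exchange-procedure harm is not hidden, because the all-causality, intra-operative and pre-exchange comparisons still show it. What is weakened is its attribution. The change is worth making, but the defect does not undermine the safety reporting as a whole.

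**What to change.** - **Protocol 9:** state that study treatment covers the drug, the implant and the study procedures (implantation, aqueous tap, exchange), and that therapeutic interventions, as another cause, excludes those procedures.
- **AE form:** add a separate relationship-to-procedure item, worded on timing from the procedure and on its known complications. Keep the existing item for the implant or drug.
- **SAP 7.1.2:** tabulate implant/drug-related and procedure-related TEAEs by study period. Count an event as treatment-related if either item is possibly, probably or definitely related.
- **Protocol 9.3:** make the two sentences refer to the same set of treatments.

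The cost is one form field, a short protocol amendment, a SAP amendment before database lock (which SAP section 1 allows) and one more table set. The reported related-event rate may rise. Any events already rated would need the new item completed retrospectively and marked as such. One limit remains: the tap and the exchange share an operating session, so a single procedure item will not separate them.

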9.1 Serious Adverse Event

Serious adverse events are defined as any findings that suggest a significant hazard, contraindication, side effect, or precaution. Any adverse event is considered a serious adverse event if it results in any of the following outcomes:

- Death
- Life- or sight-threatening
- Overnight hospitalization or prolongation of an existing hospitalization
- A persistent or significant disability/incapacity
- A congenital anomaly/birth defect

CLINICAL PROTOCOL

Date: September 18, 2019	Protocol No.: IDOS-402-IVIV
-----------------------------	--------------------------------

The terms “mild,” “moderate,” and “severe” are measures of intensity; thus a severe AE is not necessarily serious. For example, nausea of several hours duration may be rated as severe but may not be clinically serious.

Important medical events that may not result in death, be life-threatening, or require overnight hospitalization may be considered a serious adverse drug experience when, based upon appropriate medical judgment, they may jeopardize the subject and may require medical or surgical intervention to prevent one of the outcomes listed above. A life-threatening event is any event that places the subject at substantial risk of death from the event as it occurred; it does not refer to an event that hypothetically might have caused death if it were more severe. A sight-threatening event is any event that places the subject at risk of permanently losing vision in either eye as a direct result of the event.

Serious adverse events must be reported to Glaukos immediately (preferably within 24 hours of knowledge of the event).

When new significant information (including the outcome of the event) is obtained, the investigator should inform Glaukos as soon as possible. Depending on the nature of the AE, Glaukos may request copies of the ophthalmic and medical records of the subject. If the subject was hospitalized for a study-treatment related serious adverse event, a copy of the discharge summary must be forwarded to Glaukos as soon as possible.

9.2 Unexpected Adverse Event

An adverse event is considered “unexpected” if it is not listed in the investigator brochure or is not listed at the specificity or severity that has been observed, or is not consistent with the risk information described in the general investigational plan or protocol.

Unexpected adverse events must be reported to Glaukos immediately (preferably within 24 hours of knowledge of the event).

When new significant information (including the outcome of the event) is obtained, the investigator should inform Glaukos as soon as possible. Depending on the nature of the AE, Glaukos may request copies of the ophthalmic and medical records of the subject. If the subject was hospitalized for a study-treatment related unexpected adverse event, a copy of the discharge summary must be forwarded to Glaukos as soon as possible.

CLINICAL PROTOCOL

Date: September 18, 2019	Protocol No.: IDOS-402-IVIV
-----------------------------	--------------------------------

9.3 Suspected, Unexpected, Serious, Adverse Reaction (SUSAR)

A Suspected, Unexpected, Serious, Adverse Reaction (SUSAR) is any AE for which there is evidence to suggest a causal relationship between the Travoprost Intraocular Implant and the AE, and which is assessed as both unexpected and serious. An unexpected adverse reaction, i.e. any untoward and unintended response to any of the study treatments, is one for which the nature and severity is inconsistent with the applicable reference safety information (e.g., Investigator's Brochure).

9.4 Adverse Events Follow-up

Adverse events will be followed and documented until the time of complete resolution, or resolution with sequelae, or exit from the study with an assessment of the outcome.

10 MAINTAINING THE MASK

Not applicable.

11 INFORMED CONSENT

The investigator or designee will discuss the purpose and pertinent details of the study with each subject. The Informed Consent Form must be approved by the governing Institutional Review Board (IRB) or Independent Ethics Committee (IEC). Prior to undergoing any study related change in their treatment or any study related procedures, a subject must understand, sign, and date the appropriate IRB-approved Informed Consent Form. The subject's signature will be witnessed by the individual administering informed consent if other than the investigator. If the investigator administers informed consent, then the subject's signature should be witnessed by another individual (e.g., member of the site staff). The investigator will sign and date the Informed Consent Form where designated. The signed and dated Informed Consent Form will be retained with the study records, and a copy of the signed Informed Consent will be given to the subject.

